## **4. Subject Disposition**

### **4.1 Disposition**

A disposition of subjects will include the number of enrolled subjects and the number and percentage of subjects for the following categories: subjects in each analysis population, subjects who completed EOT/TOC visit (as applicable), subjects who completed the study, subjects who discontinued from the study, and the reasons for discontinuations will be presented by disease category and overall for all subjects.

The reason for study discontinuation may include any of the following: adverse event; death; disease relapse; progressive disease; lost to follow-up; physician decision; pregnancy; withdrawal by subject; other.

Subject disposition data will be presented in a listing.

### **4.2 Protocol Deviations**

The investigator may not deviate from the protocol without a formal protocol amendment having been established and approved by an appropriate IRB, except when necessary to eliminate immediate hazards to the subject or when the change(s) involve(s) only logistical or administrative aspects of the study.

Major protocol deviations will be defined in the significant protocol deviations rules document. Each significant deviation will be assigned a rule number. As the study is ongoing, additional significant protocol deviations can also be spontaneously identified or defined by the sponsor and/or the project team during the regularly planned study deviation review meetings and the significant protocol deviations rules document can be updated.

All protocol deviations will be reviewed and assessed as to significance prior to the database lock. The list of protocol deviations (major or minor) that are additionally considered major clinically relevant for the purposes of analysis will also be identified and documented prior to the database lock.

All major protocol deviations will be summarized for all enrolled subjects. Major protocol deviations will also be presented in a listing.

## 5. Demographics and Baseline Characteristics

### 5.1 Demographics

Demographics such as age, sex, race, ethnicity, BMI, and reason for enrollment will be summarized descriptively for the ITT Population. The age collected in CRF will be used for analysis if it is non-missing. If the age is not collected in the CRF, the age in years is calculated using the date of the informed consent and date of birth.

$$\text{Age (years)} = [(\text{Informed Consent Date} - \text{Date of Birth} + 1) / 365.25].$$

BMI is calculated as:

$$\text{BMI} = (\text{body weight in kilograms}) / (\text{height in meters})^2.$$

Demographics for all subjects in the ITT set will be presented in a listing.

### 5.2 Medical History

Medical history will be coded using Medical Dictionary for Regulatory Activities (MedDRA) March 2023, version 26.0 and listed by System Organ Class (SOC), Preferred Term (PT), and verbatim term. Medical history will also be summarized by disease group using frequencies and percentages with SOCs sorted in alphabetical order and PTs within each SOC in descending order of frequency for all subjects in the ITT population.

A by-subject listing of medical history will be provided.

### 5.3 Inclusion and Exclusion Criteria

Prior to enrollment, the investigator will assess if the subject fulfills all of the inclusion and none of the exclusion criteria outlined in the protocol (sections 11.1 and 11.2). The specific inclusion criterion not met or exclusion criterion which was met will be recorded in the eCRF. This information and whether the sponsor granted a waiver will be presented in a listing.

## 6. Treatment and Medications

### 6.1 Prior and Concomitant Medications

All medications (including prescription and over-the-counter medications, supplements, and herbal products) taken from 30 days before Baseline/Day 1 through TOC (Day 17) for VVC and EOT for all other fungal diseases will be recorded on the eCRF. Immunosuppressants (e.g., chemotherapy, corticosteroids, T-Cell immunosuppressants) used up to 90 days prior to subject enrollment will be recorded on the eCRF. Antifungal medications administered for the treatment of the eligible fungal infection if received for  $\geq 7$  days in the preceding 6 months prior to enrollment will also be recorded on the eCRF. In individual cases, timelines beyond 6 months or treatments less than 7 days may be requested for the record as clinically relevant, as judged by the Investigator and the Sponsor. Only the use of other antifungal medications, antibiotics for any reason or medications to treat an AE will be recorded after EOT (TOC for VVC subjects) and through the last observation in the study (35-Day FU for VVC, 6-Month FU for ABPA and 6-Week FU for all other fungal diseases). Start and stop times of concomitant medications taken during antifungal therapy will be recorded on the eCRF. Subjects will also record any new concomitant medications taken between visits in the subject diary.

All prior and concomitant medications will be coded using the current version of the World Health Organization Drug Dictionary Enhanced (WHO-DD) and summarized based on the ITT population. A by-subject listing of prior and concomitant medications will be provided.

#### 6.1.1 Prior Medications

Prior medications are defined as medications taken and stopped prior to the first dose of study drug. The number and percentage of subjects who took prior medications will be presented by WHO therapeutic drug class and generic drug name.

#### 6.1.2 Concomitant Medications

Concomitant medications are defined as medications that are ongoing at or started after the first dose of study drug and started on or before the FU visit date, regardless of whether the stop date is missing. Medications with a stop date after the first dose of study drug are also considered concomitant medications. Medications with incomplete or missing dates will be handled as detailed in [Section 3.3](#). A summary showing the number and percentage of subjects who took concomitant medications will be presented by WHO therapeutic drug class and generic drug name.

## 6.2 Study Treatments

Please refer to [Section 2.3](#) for the details of the study treatment. Data related to the study treatment will be presented in a listing.

### 6.2.1 Study Participation Calculation and Extent of Exposure

The duration of study participation (days) is calculated as date of Study Completion/Termination recorded on the End of Study page – Informed Consent date + 1. If the date of Study Completion/Termination on the End of Study page is missing, or if a subject is lost to follow-up, the latest available visit date will be used.

The duration of study treatment (days) is calculated as the date of the last dose date – the date of the first dose date + 1.

The cumulative doses taken across the treatment period for all fungal diseases will use the exposure and missed dose log. For all fungal diseases, excluding VVC, the dosing regimen is 2 doses on study days 1 and 2 and then 1 dose from study day 3 to EOT. The dosing regimen for VVC is [REDACTED]. The missed dose log will be used to subtract the total number of missed doses from these total cumulative doses.

The duration of study participation, duration of study treatment, and the cumulative doses will be summarized by summary statistics. All this exposure information will be presented in a listing.

### 6.2.2 Treatment Compliance

Treatment compliance is defined as the ratio of total study dose to the planned dose, in terms of percentage. Treatment compliance will be summarized descriptively.

Treatment compliance = the cumulative dose / the planned dose \*100%. The planned dose for all fungal diseases, excluding VVC, is defined as 2 doses for the first 2 days and then 1 dose for up to 180 days, depending on the fungal disease. The planned dose for VVC is defined [REDACTED]. The cumulative dose uses information from the missed dose log to identify missed doses.

The treatment compliance will be classified as 0, 25%, 50%, 75%, and  $\geq 100\%$ . This categorical data will be summarized with the frequency and percentage of subjects.

## 7. EFFICACY

The primary efficacy and secondary efficacy endpoints will be performed on the ITT, Myco-ITT and PP populations. The ITT analyses will be considered primary and the Myco-ITT and PP analysis will be considered supportive of the primary analyses on the ITT population.

The primary efficacy endpoint of the study is the percentage of subjects who achieve Global Response at TOC for VVC (Day 17), CMC (EOT or Day 84), CPA (EOT or Day 90) and ABPA (EOT or Day 90) (whichever comes first) and at EOT for all other diseases, as determined by the DRC. The primary efficacy endpoint will also be summarized by disease category and reason for enrollment separately. Secondary efficacy endpoints include the percentage of subjects who achieve Global Response, Clinical Response and Mycological Response by pathogen, fungal disease, disease category, and reason for enrollment at several time points as assessed by the DRC and by the Investigator. The following enrollment categories, as determined by the DRC unless stated otherwise, will be utilized: Refractory, Intolerant, Resistant (includes step-down cases), Toxicities, Relapse, Step-Down (as determined by PI). Each subject's enrollment reason will be validated by the DRC. The percentage of subjects with a recurrence, ACM and time to death will also be assessed.

Efficacy outcomes will be based on definitions captured in [Table 5](#) and [Table 6](#). Criteria for the DRC assessment of response will be further detailed in the DRC Charter. Criteria for the Investigator is outlined in [Section 7.2](#).

Efficacy evaluations will consist of clinical evaluations of the signs and symptoms of infection, mycological testing (including, but not limited to, fungal culture, KOH and other fungal stains, and T2 testing), imaging (e.g., CT, MRI, X-Ray or ultrasound) and serological testing (including, among others,  $\beta$ -D-glucan levels, GM and fungal antibody titers) as applicable for each fungal disease. Additional procedures (esophagoscopy, spirometry, St. George's Respiratory Questionnaire [SGRQ], 6-Minute Walk Test and Medical Research Council [MRC] Dyspnea Scale) will be conducted for selected fungal diseases.

Other secondary efficacy assessments will include recurrence and survival. Recurrence will be evaluated at the 6-Week FU visit after EOT for all subjects, except VVC subjects, who will be assessed for recurrence at the 25-Day FU visit. Survival status data was collected at Day 42 and Day 84. A subject's date of death will be used to determine their survival status at Day 30. Survival will be determined at Day 30 for IC/Candidemia and at Day 42 for all subjects. Additional disease-specific efficacy endpoints will be evaluated for selected fungal diseases at additional time points ([Table 7](#)).

A determination of the potential impact of protocol deviations on the efficacy-related outcomes was done by the sponsor for the purpose of defining the PPP:

- Unapproved co-administration of other systemic or topical (in case of mucosal infections) antifungal for  $\geq 10\%$  of the ibrexafungerp treatment duration or for longer than 3 days (whichever is shorter) was considered a protocol deviation warranting exclusion from the PPP.
- An EOT visit that occurred  $> 2$  weeks after last dose of ibrexafungerp for non-VVC subjects was considered a protocol deviation warranting exclusion from the PPP.

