11.3 Discontinuation Criteria

A subject may be discontinued from the study or study drug for any of the following reasons:

- Withdrawal of consent by the subject and/or subject's legal guardian;
- Investigator or Sponsor decision that withdrawal is in the subject's best interest;
- Deterioration of the clinical condition or delayed response requiring, in opinion of the Investigator, alternative therapy;
- Occurrence of an AE that, in the opinion of the Investigator, warrants discontinuation of the subject from the study drug;
- Pregnancy;
- Lost to follow up (every attempt should be made to contact the subject).

The reason for a subject's discontinuation of treatment or withdrawal from the study will be clearly documented in the source documents and on the electronic case report form (eCRF).

For VVC subjects, all TOC procedures should be performed for subjects who discontinue from the study before the TOC visit, and all 25-Day FU procedures should be performed for subjects who discontinue from the study after the TOC visit but before the 25-Day FU visit.

For all other fungal diseases, at the time of discontinuation, all EOT procedures should be performed for subjects who discontinue from treatment on or before the EOT visit and the 6-Week FU visit should also be completed. All 6-Week FU procedures should be performed for subjects who discontinue from the study after the EOT visit and on or before the 6-Week FU visit. All follow up visits should be completed for discontinued subjects regardless of need for additional antifungal therapy.

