13.2 Prohibited Medications

Medications not permitted include the following:

- Non-study systemic or topical antifungal therapy except in subject subgroups where combination therapy is allowed or where an exception was granted by the Sponsor on a per-subject basis
- Other investigational drug(s)
- Strong CYP3A4/5 inhibitors, CYP3A4/5 inducers, and select P-gp substrates (refer to Appendix B [[Section 21.2](#)] for the full list of prohibited medications).

See Appendix B [[Section 21.2](#)] for the full list of prohibited medications

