### **3.2 Analysis Populations**

The analysis populations to be used in the analysis are defined as follows:

**Intent-to-Treat Population:** The intent-to-treat (ITT) population will include all subjects who are enrolled in the study and receive at least 1 dose of study drug.

**Myco-ITT:** the Myco-ITT population will include all ITT subjects with confirmed pathogens and who also had all necessary cultures or mycology tests to estimate mycological response.

**Per-Protocol Population:** The per-protocol (PP) population will include all ITT subjects who received enough study drug (ibrexafungerp) to enable clinical efficacy judgement as determined by the DRC, who have an EOT (TOC for VVC, CMC, CPA and ABPA as applicable) assessment and who have no major protocol violations that could impact the assessment of efficacy (Refer to Section 7).

**Safety Population:** The safety population will include all subjects who receive at least one dose of study medication and have at least one safety assessment post Baseline.

**Pharmacokinetic Population:** The pharmacokinetic (PK) population will include all enrolled subjects who provide at least one PK sample and no deviations significant enough to affect the interpretability of PK data.

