	For VVC: TOC (Day 17) (Day 17, 25-Day FU [Day 32], 35-Day FU [Day 42])	For VVC: Global Response = Clinical Success , defined as at least 50% reduction from baseline in total composite score, without use of additional antifungal	For VVC: Global Response (as defined) Clinical Response : 
 
• Clinical Cure, defined as complete resolution of all signs and symptoms (VSS = 0) without use of additional antifungal (Reference FDA guidelines 2016); OR
 
• Resolved VVC infection (VSS < 3)
 
 Mycological Response : 
 
• = mycological eradication of the baseline pathogen OR
 
• Presumed eradication of the baseline pathogen Symptom resolution at FU (clinical cure, resolved infection, clinical success)
 
 Responder outcome (clinical cure and mycological eradication)

Fungal disease	Primary time point (Secondary time points)	Primary Outcome Definition	Secondary Outcome Definitions (disease-specific outcome definitions, if not previously defined) a, e
Disseminated/invasive dimorphic fungi: 
 
• Coccidioidomycosis
 
• Histoplasmosis
 
• Blastomycosis
 
	EOT (EOT, Day 42, Day 84, 6-Week FU)	Global Response = Global Response based on MSG-EORTC outcome response definitions b	Global Response (as defined) Clinical Response (including radiological outcome) and Mycological Response Clinical and Mycological Responses based on MSG-EORTC outcome response definitions b

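### The per-protocol co-administration rule removes, rather than keeps as failures, subjects given unapproved rescue antifungal that overlaps ibrexafungerp

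*SAP*

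**What the plan says.** SAP Section 3.2 limits the PP set to ITT subjects "who received enough study drug (ibrexafungerp) to enable clinical efficacy judgement as determined by the DRC", with an EOT or TOC assessment and no major violation that could affect efficacy. For the last condition it points to Section 7. The first exclusion there is "Unapproved co-administration of other systemic or topical (in case of mucosal infections) antifungal for" at least 10% "of the ibrexafungerp treatment duration or for longer than 3 days (whichever is shorter) was considered a protocol deviation warranting exclusion from the PPP". The section says that the sponsor made this determination. It gives no exception for an antifungal started because treatment was failing, and no rule for counting overlap days.

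Four other places bear on the rule:

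- Protocol 13.2 prohibits "Non-study systemic or topical antifungal therapy except in subject subgroups where combination therapy is allowed", or where the Sponsor has granted an exception for that subject.
- Protocol 11.3 lists as a reason for discontinuation "Deterioration of the clinical condition or delayed response requiring, in opinion of the Investigator, alternative therapy". For diseases other than VVC it adds that "at the time of discontinuation, all EOT procedures should be performed for subjects who discontinue from treatment on or before the EOT visit".
- SAP Table 5 defines VVC Global Response as "at least 50% reduction from baseline in total composite score, without use of additional antifungal".
- SAP Table 7 defines treatment completion in acute invasive candidiasis/candidemia so that any other antifungal treatment rules it out. SAP 7.2 presents secondary endpoints in the PP set as well as in ITT and Myco-ITT.

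SAP Section 7 makes ITT primary and PP supportive.

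**The concern.** A PP set is meant to remove subjects whose outcome says little about the study drug. A subject who worsens on ibrexafungerp and is given a second antifungal while still taking it is an informative failure. The rule does not separate that subject from one who took a second antifungal for an unrelated reason. If the overlap reaches the limit, both leave the PP set.

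Membership of the PP set can therefore depend on the outcome. The 10% limb is measured against the subject's own treatment duration, which is short when a course is cut short by failure. The trial is open-label and single-arm, so no control group is subject to the same selection. What is at stake is how much support the PP result lends to ITT: part of any agreement, or of a higher PP rate, could come from the rule itself.

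**Working it through.** **Inputs.** Let T be days of ibrexafungerp. I assume this is the SAP 6.2.1 duration: "The duration of study treatment (days) is calculated as the date of the last dose date" minus the first dose date, plus 1. Let k be whole days of overlap. Planned N is 220 (SAP 3.1, no formal calculation). The early review in Protocol 7.1 reports 20 subjects: 11 complete or partial responses, 6 stable, 2 progressions and 1 indeterminate. These add to 20, and 11/20 = 55%. The plan states no PP rate or expected number of exclusions, so there is no figure to reproduce. The 55% and the numbers excluded below are assumptions.

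**Step 1: the trigger in days.** A subject is excluded if k ≥ 0.1 × T or k > 3.

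| Course length T | Smallest k that excludes |
|---|---|
| up to 10 days | 1 |
| 11–20 days | 2 |
| 21–30 days | 3 |
| over 30 days | 4 |

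With k = 0 nobody is excluded. At T = 7 the limit is 0.7 day, so one day is enough. At T = 180 it is 4 days, or 4/180 = 2.2% of the course. Protocol 7.1 reports courses from 7 to 90 days.

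**Step 2: endpoints where the direction is fixed.** The Protocol synopsis gives VVC dosing on Days 1, 4 and 7, so T = 7 for a full course and k = 1 excludes. Table 5 already denies Global Response to anyone using an additional antifungal. Every VVC subject removed by this rule is therefore a non-success, and removal leaves the numerator unchanged. The PP rate rises or stays the same. If any day within the course counts as co-administration, an unapproved antifungal on Day 6 removes the subject. One started on Day 8, after the last dose, leaves the subject in as a non-success. The same argument applies to the acute invasive candidiasis/candidemia completion endpoint.

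**Step 3: endpoints where it is not.** SAP Table 6 does not mention other antifungals in its success or failure criteria. A subject who improves on ibrexafungerp plus an unapproved drug may be adjudicated a success, and the rule removes that success too. If m subjects are excluded, s of them successes, and ITT is x/N, then PP = (x − s)/(N − m). This exceeds ITT only when s/m < x/N. With x/N = 121/220 = 55.0% and no other exclusions:

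| m excluded | All failures (s = 0) | All successes (s = m) |
|---|---|---|
| 5 | 121/215 = 56.3% (+1.3) | 116/215 = 54.0% (−1.0) |
| 11 | 121/209 = 57.9% (+2.9) | 110/209 = 52.6% (−2.4) |
| 22 | 121/198 = 61.1% (+6.1) | 99/198 = 50.0% (−5.0) |
| 33 | 121/187 = 64.7% (+9.7) | 88/187 = 47.1% (−7.9) |

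For m = 22 the Clopper-Pearson 95% interval at the upper bound is 53.9–67.9%. If 12 of the 22 were successes, PP would be 109/198 = 55.1%, practically the ITT rate. Where the excluded subjects are all failures, keeping them in returns 55.0% in every row.

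**The case against.** A reader might infer that every failing subject who is moved to another antifungal is deleted, and that the PP rate is therefore inflated. The documents do not support that.

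- The rule concerns co-administration. Protocol 11.3 provides for the subject who stops ibrexafungerp and needs another therapy, with EOT procedures at that point for non-VVC diseases. Without overlap, the rule leaves that subject in the PP set as a failure, provided the other PP conditions are met. In VVC, an antifungal started between the last dose and TOC is likewise not caught.
- Additions approved by the Sponsor are outside the rule.
- Treating a same-day stop and start as one day of overlap is a reading. The SAP does not say how days are counted, and start and stop times are recorded.
- Outside the two endpoints in Step 2 the rule also removes successes that a second drug may have produced, which is an ordinary purpose of a PP set.
- The low trigger for short courses is in days only. As a share of treatment, the limit is tightest for long courses, which also allow more time for overlap to build up.

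All of this stands, and it narrows the point. It does not supply the missing exception. Two equally failing subjects are still handled differently according to whether their drug dates overlapped, and for the two endpoints in Step 2 the effect has only one direction.

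**Conclusion.** The concern holds in a limited form. Unapproved rescue that overlaps ibrexafungerp removes a subject from the PP set whatever the reason for it, and nothing in the plan keeps failure-driven cases in. For VVC Global Response and for completion in acute invasive candidiasis/candidemia, this can raise the PP rate but cannot lower it. For the EORTC-MSG diseases the direction is unknown. The illustration of +6.1 to −5.0 points rests on an assumed 55% ITT response and an assumed 22 of 220 excluded, and its ends are the extreme cases in which all those excluded are failures or all are successes. The documents do not say how many subjects had such overlap or how they were scored.

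The primary ITT estimate is not touched. The weakness lies in an analysis designated as support, so the change is worth making but the primary result does not depend on it.

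**What to change.** Amend the first exclusion in SAP Section 7 in three ways.

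1. Add: subjects whose other antifungal was started for lack of response, progression or worsening of the baseline fungal disease stay in the PPP with their DRC-adjudicated outcome (non-success in VVC, per Table 5); only other unapproved co-administration leads to exclusion.
2. State how overlap days are counted, and that the calendar day of a switch is not co-administration.
3. Report the number of subjects excluded under this rule and their ITT outcomes, by disease category.

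Retained subjects should not be scored automatically as Global Response failures outside VVC, because that would override the DRC and change the endpoint.

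The cost is a short SAP edit and a review of why each other antifungal was started. Antifungal use, start and stop times and discontinuation reasons are already collected, but a discontinuation reason will not explain every added drug, so some cases will need a source check. The PP rate may fall, and some retained subjects will have outcomes influenced by a second drug.

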18.4.2 Efficacy Assessments

Response will be assessed by the DRC and by the Investigator. The primary efficacy endpoint of the study is the percentage of subjects who achieve Global Response at TOC for VVC (Day 17), CMC (Day 84), CPA (Day 90), ABPA (Day 90) and at EOT for all other diseases, as determined by the DRC. In cases where EOT for CMC, CPA or ABPA subjects occurs before the planned TOC days, EOT will be TOC assessment. Secondary efficacy endpoints include the percentage of subjects who achieve Global Response, Clinical Response and Mycological Response by pathogen and by disease category (type of fungal disease) at several time points as assessed by the DRC and by the Investigator. The percentage of subjects with a recurrence, ACM and time to death will also be assessed. See [Section 9.0](#) for detailed study endpoints and [Section 14.2](#) for efficacy procedures.

Efficacy outcomes will be based on the definitions captured in [Table 16](#) and [Table 17](#). Criteria for the DRC assessment of response will be further detailed in the DRC Charter. Criteria for the Investigator is outlined in [Section 18.4.5](#).

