### 7.1.1 Primary Analysis

The primary efficacy analysis will be performed at TOC for VVC (Day 17), CMC (EOT or Day 84), CPA (EOT or Day 90) and ABPA (EOT or Day 90) whichever comes first, and at EOT for all other diseases. For CMC, CPA, and ABPA, if Day 84 or Day 90 is the earlier visit and the Global Response is not evaluable or was not done, and the EOT visit has a Global Response, then the EOT information will be used. The number and percentage of subjects with Successful Global Response as determined by the DRC will be presented separately for each fungal disease, disease category, enrollment category, and pathogen along with a 95% confidence interval (CI) for a single binomial proportion in the ITT and PP populations. The Clopper Pearson method will be used for the confidence interval. CI will not be estimated when the subjects in a particular disease, disease category, enrollment category, or pathogen is less than 5. In addition, the overall response will be presented for all disease categories combined.

The following disease categories and fungal diseases will be used for the analysis.

- Acute invasive candidiasis (IC), including candidemia
  - Acute IC with/without candidemia
  - Candidemia only
- Chronic candidiasis
  - Chronic IC
  - Chronic mucocutaneous candidiasis (CMC)
- Mucocutaneous candidiasis
  - OPC (including oropharyngeal, laryngeal)
  - EC
  - VVC
- Disseminated /invasive dimorphic fungi
- Aspergillus syndromes
  - CPA
  - ABPA
  - IPA
- Other emerging fungi

The following pathogens will be used for the analysis.

- Invasive Candidiasis, including candidemia
  - Albicans
  - Auris
  - Glabrata
  - Krusei
  - Parapsilosis
  - Tropicalis

- Other Candida species
- Mucocutaneous Candidiasis (CMC, OPC, EC, VVC)
  - Albicans
  - Auris
  - Glabrata
  - Krusei
  - Parapsilosis
  - Tropicalis
  - Other Candida species
- Dimorphic fungi
  - Coccidioidomycosis
  - Histoplasmosis
  - Blastomycosis
  - Other Dimorphic fungi species
- Aspergillus Syndromes (CPA, ABPA, IPA)
  - Flavus
  - Fumigatus
  - Nidulans
  - Terreus
  - Other Aspergillus species

Invasive Candidiasis will be grouped according to the following sites of infection:

- Pleural/Pulmonary
- Intraabdominal / Pelvic
- Soft tissue/wound
- Endovascular/endocarditis
- Mediastinitis
- Osteomyelitis
- Native joint
- Prosthetic joint
- Urinary tract
- Other

The following enrollment categories (as determined by DRC unless otherwise stated) will be used for the analysis.

- Refractory

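### For CMC, CPA and ABPA subjects treated beyond Day 84/90 with an evaluable TOC response, the per-protocol timing exclusion tests the EOT visit, which does not supply their primary response

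*SAP*

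**What the plan says.** SAP Section 7 gives two deviations that the sponsor judged to warrant exclusion from PP: unapproved use of another antifungal, and late EOT. The second covers an EOT visit more than 2 "weeks after last dose of ibrexafungerp for non-VVC subjects was considered a protocol deviation warranting exclusion from the PPP". It makes no separate provision for CMC, CPA or ABPA.

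The same section sets the primary time point for those diseases as "CMC (EOT or Day 84), CPA (EOT or Day 90) and ABPA (EOT or Day 90) (whichever comes first"). Protocol Section 18.4.2 covers early stopping: "In cases where EOT for CMC, CPA or ABPA subjects occurs before the planned TOC days, EOT will be TOC assessment". SAP Section 7.1.1 adds a fallback. The EOT response is used, where there is one, "if Day 84 or Day 90 is the earlier visit and the Global Response is not evaluable or was not done".

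The PP definition in SAP Section 3.2 admits subjects "who have an EOT (TOC for VVC, CMC, CPA and ABPA as applicable) assessment" and requires "no major protocol violations that could impact the assessment of efficacy (Refer to Section 7"). SAP Section 4.2 adds a deviation rules document and a review of deviations before the data are locked: "The list of protocol deviations (major or minor) that are additionally considered major clinically relevant for the purposes of analysis will also be identified".

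**The concern.** A PP timing rule should protect the assessment being analysed. Section 3.2 recognises that for CMC, CPA and ABPA this is the TOC assessment. The Section 7 rule looks at EOT instead. For a subject treated well past Day 84/90 these are different visits, and a late EOT visit cannot alter a response already assessed at Day 84/90.

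Such a subject can leave the primary PP analysis for a reason that has nothing to do with the primary response. At stake are the PP response rates for CMC, CPA and ABPA, the rates for the disease categories that contain them, and the combined PP rate.

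**Working it through.** No figure in the plan depends on this rule, so there is none to reproduce. The check applies the stated rules to hypothetical subjects.

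**Inputs**
- Timing exclusion: EOT visit more than 14 days after last dose, all non-VVC subjects (SAP Section 7).
- Scored visit: EOT if treatment ends before day T, otherwise the Day T visit, where T = 84 for CMC and 90 for CPA and ABPA (SAP Sections 7 and 7.1.1; Protocol Section 18.4.2). EOT replaces Day T if Day T is not evaluable or not done (SAP Section 7.1.1).
- Windows: Day 84 and Day 90 ±7 days, EOT ±3 days (Protocol Table 9; SAP Table 3).
- Treatment: up to 180 days, extendable with sponsor approval (SAP Section 2.3). EOT can therefore fall 180 − 90 = 90 days or 180 − 84 = 96 days after the scored visit, or later.
- Subjects in these diseases still on treatment at database lock contribute data up to TOC (Protocol Section 18.3).

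**Rule:** excluded if (EOT visit day − last dose day) > 14.

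| Hypothetical subject | Scored visit | Timing of scored visit | EOT visit − last dose | Effect of the rule |
|---|---|---|---|---|
| A: CPA, Day 90 visit on Day 90, evaluable; last dose Day 180; EOT visit Day 195 | Day 90 | 90 − 90 = 0 days off | 195 − 180 = 15 | Excluded, although the scored visit is on time |
| B: CMC, Day 84 visit on Day 84, evaluable; last dose Day 180; EOT visit Day 195 | Day 84 | 84 − 84 = 0 days off | 15 | Excluded, although the scored visit is on time |
| C: CPA, last dose Day 60; EOT visit Day 76 | EOT | 16 days after last dose | 76 − 60 = 16 | Excluded, on target |
| D: CPA, last dose Day 60; EOT visit Day 61 | EOT | 1 day after last dose | 61 − 60 = 1 | Kept, on target |
| E: as A, but Day 90 not evaluable | EOT, by fallback | 15 days after last dose | 15 | Excluded, on target |
| F: CPA, Day 90 visit on Day 90, evaluable; still on treatment at lock | Day 90 | 0 days off | No EOT visit yet | Not touched by this rule |

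The rule misses its target in A and B only. A and F have the same primary data, yet only A is excluded. ABPA behaves as CPA does.

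**Size.** The documents give no category counts, so these are assumed. Dropping one subject changes x/n to (x − 1)/(n − 1) if a responder is lost, or to x/(n − 1) if a non-responder is lost. Intervals are Clopper-Pearson, the SAP's method.
- n = 10, 60%: 6/10 = 60.0% (95% CI 26.2 to 87.8). It becomes 5/9 = 55.6% (21.2 to 86.3), down 4.4 points, or 6/9 = 66.7% (29.9 to 92.5), up 6.7.
- n = 20, 60%: 12/20 = 60.0% (36.1 to 80.9). It becomes 11/19 = 57.9%, down 2.1 points, or 12/19 = 63.2%, up 3.2.
- Two dropped at n = 10: 4/8 = 50.0% (15.7 to 84.3) if both responded, 6/8 = 75.0% (34.9 to 96.8) if neither did.
- Two dropped at n = 20: 10/18 = 55.6% (30.8 to 78.5) or 12/18 = 66.7% (41.0 to 86.7).

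**The case against.** **The EOT rule has a purpose in these diseases.** EOT is the primary visit when treatment ends before Day 84/90 or when the fallback applies, and there the rule is right (C, D and E). EOT is also a listed secondary time point for all three diseases (SAP Table 5), and secondary endpoints are analysed in PP (SAP Section 7.2). Recurrence is defined from the response at EOT (Protocol Section 18.4.2.2), and follow-up visits are counted from EOT (Protocol Section 14.0). This all stands. It supports excluding a late-EOT subject from PP analyses of EOT-based endpoints. It does not support removing an evaluable Day 84/90 response from the primary PP analysis.

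**Other deviations can be handled outside Section 7.** A reader might infer that badly mistimed TOC visits stay in PP, because Section 7 gives no timing limit for the Day 84/90 visit or for the VVC Day 17 (±3) visit. The documents do not establish that. Section 4.2 allows further deviations to be defined in a rules document and a list fixed before lock, and neither is among the documents reviewed. Nor is it stated that a visit far outside the Day 90 window would be analysed as Day 90. A visit on Day 130 lies within the Day 120 ±14 window (106 to 134), and if Day 90 then counts as not done, the fallback moves scoring to EOT. So this is only a gap in the Section 7 list. Section 4.2 can add exclusions, but nothing in it reverses the stated one that removes A and B.

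**The consequence is small.** PP is supportive, ITT is primary and the study is exploratory. Exclusion also needs an EOT visit more than 14 days after last dose, against a ±3 day window. This stands and limits the weight of the point.

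**Conclusion.** The point holds for CMC, CPA and ABPA subjects treated beyond Day 84/90 who have an evaluable TOC Global Response. For them the Section 7 exclusion tests a visit that does not supply the primary response, contrary to the TOC wording of Section 3.2. They can be dropped from the primary PP analysis despite a valid, on-time assessment.

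It does not follow that all three diseases are always scored at Day 84/90, or that every subject treated beyond TOC is at practical risk. The number affected is not given.

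On an assumed n of 10 to 20 and a 60% rate, one exclusion moves a PP rate by about 2 to 7 points, well inside the confidence interval. A shift of 5 to 10 points from one subject is a ceiling. It arises only if the subject dropped is the sole responder or sole non-responder, for example 19/20 to 19/19 (+5) or 9/10 to 9/9 (+10). No ITT result changes.

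**What to change.** In SAP Section 7, for the primary PP analysis, tie the timing exclusion to the visit that supplies the primary Global Response:
- **EOT relative to last dose** where EOT is the primary time point. This includes CMC, CPA and ABPA subjects who stop before Day 84/90 and those scored at EOT under the Section 7.1.1 fallback.
- **The Day 84/90 visit relative to its scheduled day** otherwise. State the tolerance; the documents give a ±7 day visit window but no PP limit.
- **No exclusion on EOT timing** when an evaluable Day 84/90 response is used. A late EOT may still exclude the subject from PP analyses of EOT-based secondary endpoints.

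Also state, or cross-refer to the deviation rules document for, whether any timing limit applies to the Day 84/90 visit and the VVC Day 17 visit.

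The cost is a SAP wording change, a rerun of the PP flag from recorded visit and last-dose dates, and one additional endpoint-specific flag for EOT-based secondary endpoints. Section 7 describes the sponsor's determination in the past tense, so flags already assigned should be rechecked. No new data are needed.
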